#### Methodology:

Twelve healthy patients with 24 carious molar teeth will be selected where each patient should have two ocluso- mesial cavities. Standardized

occluso- mesial cavities will be prepared for all the selected teeth, for each patient the first tooth will be restored with conventional nanohybrid RBC (M1). Meanwhile, the second tooth will be restored by self-cure bioactive RBC (M2). Then, wear resistance will be evaluated by intraoral scanner immediately after restoration (T0), six months later (T1), after 12 months (T2), 18 months (T3) and 24 months (T4). Software analysis will be done by superimposing the 3D digital impression and evaluate the restoration wear by calculating the 3D volume loss.

Also, bioactivity of the restoration will be measured by measuring the mineral density beneath the restoration. Digital radiographic images will be taken for the restoration by parallel technique and grey scale of the pixels under restoration will be measured by software immediately after restoration (D0), one month later (D1) and after 3 months (D2).

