### **II-4 Randomization:**

To minimize selection bias and ensure equal distribution of treatment protocol across both treated molars, simple randomization will be used to randomly determine which molar receives which material. Therefore, randomization will be performed using an online randomization tool (<https://www.randomizer.org/>) prior to treatment allocation where, each patient will be given a unique study number, ensuring that each patient receives both treatments in a randomly assigned manner.

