## II-5 Restorative procedures:

Each included patient with the already prepared cavities will receive two different types of restorations. where one of them will be restored with light cured nano hybrid RBC (Filtek™ Z250, 3M ESPE St.Paul,M,USA) (M1) meanwhile, the second cavity will be restored with self-cure bioactive RBC (Stela, SDI, Australia) (M2).

A sectional matrix system will be used to achieve proper proximal contour and anatomically correct contact with the adjacent tooth. Then, the restorative procedure of each cavity will be carried out according to the manufacturer's recommendations of each tested restoration. Before restoration each cavity will be carefully cleaned with copious air water spray before being dried. Restoration of (M1) group will be performed through selective etching of the prepared cavity enamel surface using 37% phosphoric acid gel (Meta Biomed, Korea) for 15 seconds. This will be followed by rinsing with water for 15 seconds and gentle air drying for 5 seconds, leaving the cavity slightly moist. After that, single layer of a universal adhesive bonding agent (Bisco, INC Schaumburg, IL, USA) will be applied to the prepared cavity walls and floor using disposable adhesive micro brush. The adhesive will be subsequently cured for 20 seconds using LED light curing unit (Elipar S10, 3M ESPE, St Paul, Minnesota, USA) with an intensity of 1200 mW/cm^2. The nano hybrid RBC (Filtek™ Z250) will be incrementally applied, and light cured according to manufacturer instructions. Finally, finishing and polishing of the restoration using one-step polishing system (Dimanto, Voco, Germany). Then, checking of occlusion and proximal contacts will be done.

Restoration of (M2) group will be performed through conditioning of cavities with a specialized primer (STELA primer, SDI, Australia) according to manufacturer instructions. Then, a self cured bioactive RBC (STELA, SDI, Australia) will be placed in a single increment and allowed to self-cure according to manufacturer instructions. Then, finishing and polishing of the restoration, checking the occlusion and proximal contacts will be done as mentioned before.

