## 6- Sample size calculation:

Sample size calculation was performed using G\*Power version 3.1.9.2, (Faul *et al*, 2007) University Kiel, Germany. Copyright (c) 1992-2014.

$$f = \frac{\sigma_\mu}{\sigma}$$

[figure not shown]
$$\sigma_\mu^2 = \frac{\sum_{i=1}^k n_j (\mu_i - \mu)^2}{N}$$

Where:

$f$ : is the effect size;  $\alpha = 0.05$ ;  $\beta = 0.05$ ; Power =  $1 - \beta = 0.80$

The effect size  $d$  was **1.22 (large)** according to the previous studies (**Elderiny et al., 2024**) with alpha ( $\alpha$ ) level of 0.05 and Beta ( $\beta$ ) level of 0.05, i.e., power = 80%; the estimated sample size ( $n$ ) should be **20** samples and will be divided into **two groups**.

To account for dropouts, the sample size will be expanded by 20%, which produced 12 restorations for each group instead of 10.

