### Statistical analysis:

All collected data will be calculated, tabulated, and statistically analyzed using suitable statistical tests as follows: **A normality test:** will be done to check normal distribution for data by Shapiro-Wilk test. **Descriptive statistics:** will be calculated in the form of mean  $\pm$  standard deviation (SD), range (Max-Min). Qualitative data will be presenting as (%) frequencies (n) and percentages. **T- test or Mann-Whitney test**

**(According to the types of data).** Independent Student's T-test or Mann-Whitney will be performed for pair wise comparison between groups in each time at P value < 0.05. **The Chi-square test** will be used to test significance of association between categorical variables. **Pearson's correlation coefficient:** will be used for estimating the relationship between quantitative variables. **P<0.05** is considered significant. Statistical analysis will be performed using the computer program SPSS software for windows version 26.0 (statistical package for social science, ARMONK, NY: IBM Corp).

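### Every patient receives both materials, yet the plan compares the materials with tests for independent groups; the between-material analysis should be paired.

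*Protocol*

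**What the plan says.** The design is within-patient throughout. The Methodology part of the Abstract says "Twelve healthy patients with 24 carious molar teeth will be selected where each patient should have two ocluso- mesial cavities". Section II-4 (Randomization) only decides which of a patient's two molars receives which material, "ensuring that each patient receives both treatments in a randomly assigned manner". Section II-5 (Restorative procedures) repeats it: "Each included patient with the already prepared cavities will receive two different types of restorations".

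For the comparison of the two materials, the Statistical analysis section specifies "Independent Student's T-test or Mann-Whitney will be performed for pair wise comparison between groups in each time at P value < 0.05". No paired t-test, Wilcoxon signed-rank test, repeated-measures analysis or mixed model appears anywhere in the protocol.

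Section 6 (Sample size calculation) treats the data the same way. It uses an effect size that "was 1.22 (large) according to the previous studies" and arrives at 20 samples split into two groups, raised from 10 to 12 restorations per group for dropout.

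**The concern.** The independent t-test and the Mann-Whitney test both require the M1 and M2 observations to be independent. Here each M1 tooth has an M2 partner that shares the patient's bite force, diet, saliva, hygiene and imaging conditions, so positive correlation is expected for both wear volume and mineral density. The independent test ignores that correlation and puts the whole between-patient variance into the standard error of the material difference.

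The affected test serves both study objectives at every follow-up visit. The stated null hypothesis is no significant difference, and the trial has only 10 to 12 patients. An over-conservative test therefore makes a mistaken finding of no difference more likely. Section 4d expects only a slight wear disadvantage for the bioactive material, the kind of effect for which lost power matters most.

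**Working it through.** **Inputs from the protocol.** 12 patients and 24 teeth (Abstract, Methodology); 10 per group before dropout and effect size d = 1.22 (Section 6); significance level 0.05 (Statistical analysis). **Assumed.** Within-patient correlation r, which the protocol does not give: 0.3, 0.5 and 0.7, with r = 0 and negative r for contrast. Normal data, equal variances, two-sided tests except where stated. A difference of 0.8 SD is also an assumption, added to show an effect smaller than 1.22.

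**The plan's own figure.** Noncentral-t power for two independent means with d = 1.22 at 0.05:
- One-sided: 9 per group gives 79.7% and 10 per group gives 83.6%, so 80% power needs 10 per group, N = 20, as stated.
- Two-sided: 10 per group gives 73.2%, and 80% power needs 12 per group.

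The stated 20 is thus reproduced exactly by a one-sided t-test for independent groups. The sample size, like the analysis, can be read as ignoring the pairing.

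**Standard error.** With n pairs and tooth-level variance σ², the mean difference has true variance 2σ²(1 − r)/n. The independent test estimates 2σ²/n. Its standard error is therefore too large by 1/√(1 − r): 1.20, 1.41 and 1.83 for r = 0.3, 0.5 and 0.7.

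**Confidence interval.** With 10 pairs, the ratio of independent to paired interval width is approximately [t(0.975, 18) / t(0.975, 9)] / √(1 − r) = (2.101/2.262)/√(1 − r) = 0.929/√(1 − r), which gives 1.11, 1.31 and 1.70.

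**Type I error and power.** The paired test has standardised effect dz = d/√(2(1 − r)), noncentrality dz√n and n − 1 degrees of freedom. For d = 1.22, dz is 1.03, 1.22 and 1.58. The independent test was evaluated by simulating correlated normal pairs (400,000 trials per setting at d = 0 and 1.22; 60,000 for the 0.8 SD column with 10 pairs, 200,000 with 12).

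| Pairs | r | Type I error, independent | Power at d = 1.22, independent vs paired | Power at 0.8 SD, independent vs paired |
|---|---|---|---|---|
| 10 | 0.3 | 2.2% | 76.5% vs 82.6% | 38% vs 48% |
| 10 | 0.5 | 0.9% | 79.5% vs 92.9% | 37% vs 62% |
| 10 | 0.7 | 0.2% | 83.4% vs 99.3% | 35% vs 83% |
| 12 | 0.3 | 2.2% | 85.1% vs 90.0% | 46% vs 57% |
| 12 | 0.5 | 0.9% | 88.4% vs 97.0% | 46% vs 71% |
| 12 | 0.7 | 0.2% | 92.3% vs 99.9% | 45% vs 90% |

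The paired test keeps its type I error at about 5.0% in every setting.

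**Boundary cases, d = 1.22, 10 pairs.** At r = 0 the independent test is valid (5.0%) and slightly more powerful (73% vs 68%), because the paired test has 9 degrees of freedom instead of 18. By r = 0.2 the paired test is already ahead (77.5% vs 75.3%). At r = −0.2 the independent test would be too liberal (7.1%).

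**The case against.** The phrase pair wise in the analysis sentence might be taken to mean a paired test. It does not: the sentence names the independent t-test and its unpaired rank counterpart, so pair wise can only mean M1 against M2.

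Stronger objections concern size and direction:
- At the effect for which the trial was sized, the loss is moderate: about 6 to 16 percentage points with 10 pairs and 5 to 9 with 12. With all 12 pairs retained, the planned test stays above 80% power over the assumed range of r. This stands. The larger losses belong to smaller effects.
- Under positive correlation the error is conservative. It creates no false positive claims, leaves the estimated mean difference unchanged when pairs are complete, and could be corrected later from the same data. This also stands, but it does not justify fixing the wrong test in advance.
- The Statistical analysis section plans no confidence intervals, so the width ratio applies only if intervals are reported. This stands.
- The fault concerns the M1-versus-M2 tests. The descriptive statistics are unaffected, and the Pearson correlation is not a comparison between materials. A chi-square comparison of the materials would share the fault.

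None of these reconciles an independent-groups test with a split-mouth design. Nor is this a detail left to a statistical analysis plan: the protocol names a specific test, and it does not fit.

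**Conclusion.** Wrong as written. The contradiction between design and test is explicit and does not depend on any assumed number. Its size does. For r from 0.3 to 0.7, normal data and 10 pairs, the nominal 5% test really operates at about 2% down to 0.2%. Power falls by about 6 to 16 points at d = 1.22, and by about 10 to 48 points at 0.8 SD. Only if r is close to zero does the planned test do no harm, which is implausible for two molars in one mouth. The expected consequence is a real difference in wear or mineral density reported as non-significant.

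**What to change.** In the Statistical analysis section, replace the independent t-test or Mann-Whitney test with a paired t-test on the within-patient difference M2 minus M1, or a Wilcoxon signed-rank test if the differences are clearly non-normal. A linear mixed model with a patient random effect is an alternative. It matches the paired t-test when pairs are complete and the estimated patient variance is not negative, and it can also use patients with one tooth missing.

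Three changes follow:
- Apply the Shapiro-Wilk test to the within-patient differences, and report the mean paired difference with its 95% confidence interval.
- Replace any chi-square comparison of the materials with a matched-pairs test such as McNemar's.
- Restate Section 6 in pairs, with an assumed r and the sidedness of the test. For a two-sided paired t-test at 80% power and d = 1.22 between teeth, the requirement before dropout is 13 pairs at r = 0, 11 at 0.2, 10 at 0.3, 8 at 0.5 and 6 at 0.7.

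The cost is a few sentences of text. No extra patients, visits or measurements are needed. The only statistical price is the loss of degrees of freedom from 18 to 9 with 10 pairs, about 5 power points at d = 1.22 if r were zero.

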#### **II-7- Assessment of the bioactivity:**

Bioactivity of each examined restoration will be determined by the evaluation of mineral density beneath the tested materials. Immediately after restoration (D0), an image plate digital sensor (Xios XG Supreme, Dentsply Sirona, UK) will be used for transmitting the radiographic

image of the selected tooth to the computer. A posterior parallel kit will be used for image standardization. Later, each restoration will be examined at standardized follow-up periods; one month (D1) and three months (D2) (Table 4 and 5). The image plate will be inserted at one end of the parallel kit, while the other end was connected to the x-ray cone. All the radiographs will be evaluated for the outcome by a software (ImageJ software, NIH, USA). The assessment of mineral density will be done by the software through performing the following measurements: in each image a line will be drawn along the CEJ to act as a reference, while another parallel line will be drawn at the bottom of the cavity. The distance between both lines will be standardized for each tooth by measuring the length of a vertical line connecting them. The length of the line centralized at the bottom of the cavity will be determined in pixels directly via the previously mentioned software. Such length will be fixed for each sample throughout assessment intervals. Three points on this line (at its start, middle and end) will be determined. The mineral density value at each of these points will be identified by taking the corresponding three readings from the software and recording them to calculate the average value. The mineral density mean value will be calculated from the software (Ibrahim et al, 2016).

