**Table 4: Variables of the bioactivity test and levels of investigations:**

Variable	Level	Referred to
Type of material (M).	M1	Light cured nanohybrid RBC.
	M2	Self-cured bioactive RBC.
Time of follow-up for mineral density (D).	D0	Immediately after restoration.
	D1	After one month.
	D2	After three months.

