**Table 5: Interaction between variables for bioactivity test:**

M		Type of material (M)		Total
		M1	M2	
Times (D)	D0	M1D0	M2D0	
	D1	M1D1	M2D1	
	D2	M1D2	M2D2	
Total		10	10	20

Sample size: n= 10

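### The Statistical analysis section tests the materials as independent groups although each patient receives both, and the research question asks for two-year bioactivity from three-month radiographs

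*Protocol*

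**What the plan says.** **Design.** The Abstract (Methodology) plans twelve patients with 24 molars, two per patient. Section II-3 places the two cavities on both sides of the mouth. Section II-4 randomises which molar receives which material, "ensuring that each patient receives both treatments in a randomly assigned manner". Section II-5 agrees: "Each included patient with the already prepared cavities will receive two different types of restorations". The protocol does not use the term split-mouth, but that is the design it describes.

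**Analysis.** The only between-material test of a quantitative outcome is this: "Independent Student's T-test or Mann-Whitney will be performed for pair wise comparison between groups in each time". The section's other tests are Shapiro-Wilk, chi-square and Pearson correlation. None is a paired or repeated-measures test. The sentence is not limited to one outcome, so it governs both wear volume and mineral density.

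**Sample size.** Section 6 gives d = 1.22 and 20 samples in two groups, then a 20% expansion, "which produced 12 restorations for each group instead of 10".

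**Time horizon.** Section 3 (Research Q) asks about wear resistance and bioactivity together at two years. Section II-7 sets the radiographs after D0 at "one month (D1) and three months (D2". The Abstract and Tables 4 and 5 also stop at three months. Only the wear scans (section II-6) reach 24 months.

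**The concern.** An independent-samples test sets the standard error of the difference as if the two teeth came from different people. Here they share a mouth, a diet, an oral hygiene regime and an examiner. Part of the spread between readings is therefore likely to be spread between patients, which cancels from a within-patient comparison. The named test keeps that spread in its error term. With only 10 to 12 pairs, this may be enough to miss a difference between materials that the same readings would show in a paired test.

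The time horizon raises a different problem. As written, part of the research question has no data behind it, and a reader of the final report could take a three-month density result for a two-year finding.

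**Working it through.** **Inputs.** From section 6: d = 1.22, alpha 0.05, power 80%, 10 restorations per material before expansion and 12 after. Assumed: normal data with SD 1 per tooth, a two-sided test, a between-tooth correlation ρ within patient of 0 to 0.5, and a second, smaller effect of 0.8 SD. The protocol gives no correlation and does not tie d = 1.22 to either outcome in particular.

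**1. The plan's own figure.** An independent two-sample t-test with d = 1.22 and 80% power needs 10 per group one-sided (power 0.836), which matches the stated 20. Two-sided, it needs 12 per group, and 10 per group gives power 0.732. A paired t-test with a standardised mean difference of 1.22 would need 6 pairs (one-sided) or 8 pairs (two-sided), which does not match. The sample size thus fits the independent-groups analysis, and neither uses the pairing.

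**2. Why the independent test is conservative.** The true variance of the difference in means is 2σ²(1 − ρ)/n; the independent test works with 2σ²/n. At ρ = 0.3 the true standard error is √0.7 = 0.837 of the assumed one. The critical value t₁₈ = 2.101 then acts like 2.101/0.837 = 2.51, which has a two-sided tail of about 2.2%.

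**3. Power of the paired test.** The effect on the scale of the differences is d/√(2(1 − ρ)). At ρ = 0.3 this is 0.8/√1.4 = 0.676 or 1.22/√1.4 = 1.031. With 10 pairs (9 degrees of freedom) the noncentral t gives 48% and 83%.

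**4. Comparison.** Simulation, 200,000 runs, two-sided 5%:

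| Pairs | ρ | Type I error, independent | Power at 0.8 SD, independent v paired | Power at d = 1.22, independent v paired |
|---|---|---|---|---|
| 10 | 0 | 5.0% | 40% v 36% | 73% v 68% |
| 10 | 0.1 | about 4% | 39% v 39% | 74% v 73% |
| 10 | 0.3 | 2.2% | 38% v 48% | 76% v 83% |
| 10 | 0.5 | about 1% | 37% v 62% | about 80% v 93% |
| 12 | 0.3 | 2.2% | 46% v 57% | 85% v 90% |

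The Mann-Whitney alternative does no better: with 10 pairs and ρ = 0.3 its type I error is 1.9% and its power 34% and 72% (20,000 runs).

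**5. What pairing costs.** Error degrees of freedom fall from 18 to 9 with 10 pairs. The paired interval is the narrower one only if ρ exceeds 1 − (t₁₈/t₉)² = 1 − (2.101/2.262)² = 0.14. With 12 pairs the threshold is 1 − (2.074/2.201)² = 0.11.

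**6. Time horizon.** No arithmetic is needed. The question is set at 24 months and the last density reading is at month 3, which leaves 21 months without a bioactivity measurement.

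**The case against.** **Is it only a loose phrase?** The section opens with a promise of suitable tests and speaks of pairwise comparison. But that promise introduces the list that follows, and pairwise there means one material against the other. The tests named are the independent-samples ones, so the protocol has fixed the choice and not left it to an analysis plan.

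**The size is unknown.** This stands. Every correlation above is assumed, as is the 0.8 SD effect. At ρ near zero the independent test is slightly better. A reader might infer that ignoring the pairing produces false positives. With positive correlation it does the opposite: the cost is power, not error control.

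**No test of change from D0.** A reader might go further and say that the bioactivity analysis is wrong because no test addresses change in density, the more so as section II-7 standardises the measured line over time: "Such length will be fixed for each sample throughout assessment intervals". The protocol does not support that. Its objective is a comparison of materials. Molars are randomised, so unless the material itself affects the image, the difference at D2 already estimates the difference in change. The argument that a constant grey-level offset from the material would distort D2 rests on an assumption found nowhere in the protocol. Adjusting for D0 is not a sure gain either: with 10 pairs and ρ = 0.3, depending on the assumed D0–D2 correlation and its structure, it changes the variance of the paired comparison by anything from +14% to −78%. The absence of a change analysis is not an error.

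**The two-year wording is a slip.** Probably so, since the Abstract, section II-7 and Tables 4 and 5 agree on three months. But it stands in the research question, where it sets what the trial claims to answer.

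**Conclusion.** The concern holds in two parts.

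First, the named between-material test does not fit the design. This follows from the text alone and applies to wear as much as to density. Its consequence depends on the unknown within-patient correlation: nothing is lost at 0.1, about 10 percentage points of power at 0.3 and 25 at 0.5 for a 0.8 SD effect with 10 pairs (48 − 38 and 62 − 37). At d = 1.22 the loss is about 7 and 13 points (83 − 76 and 93 − 80). A significant result from the named test would not be discredited. A non-significant one would be hard to interpret.

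Second, no two-year conclusion on bioactivity can be supported, because density is not measured after three months. This needs no assumption.

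The point is one to correct before analysis. It does not undermine the trial.

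**What to change.** **Statistical analysis section.** For wear and density, replace the independent t-test or Mann-Whitney test with a within-patient comparison of materials at each time. This can be a paired t-test on the within-patient differences or a mixed model with patient as random effect. Check normality on the differences and name the Wilcoxon signed-rank test as the fallback. The fallback is usable at this size: with 10 pairs and no ties the smallest exact two-sided p-value is 2/2¹⁰ = 0.002.

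**Optional.** The paired change in density from D0 may be reported as a supportive analysis from readings already planned.

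**Research question (section 3).** Restate it as wear at two years and radiographic mineral density at three months.

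**Abstract.** Read literally, its Methodology gives the nanohybrid to the first tooth of every patient, whereas section II-4 assigns the material at random. The two passages must be reconciled; if first is only a label, say so.

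**Cost.** Wording only, with no added visit, scan or radiograph. The statistical price is half the error degrees of freedom, and a slight loss of precision if the correlation is below about 0.14 with 10 pairs.

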The manufacturer claimed that **Stela** is an innovative bioactive material with high strength properties. It offers an unlimited depth of cure and low-stress polymerization with a gap-free interface (**SDI Limited, 2023**). Therefore, the primary objectives of this study are to clinically evaluate the wear resistance and the bioactivity of such material.

Wear behavior of a micro hybrid composite vs. a nanocomposite in the treatment of severe tooth wear patients was evaluated. A convenience sample of 16 patients with severe tooth wear was chosen. Eight of them were treated with a micro hybrid composite (Clearfil APX, Kuraray) and the other eight with a nanocomposite (Filtek Supreme XTE, 3M). The Direct Shaping by Occlusion (DSO) technique was used for all patients. Clinical records were collected after 1 month (baseline) as well as 1-, 3- and 5-years post-treatment. The maximum height loss at specific areas per tooth was measured with Geomagic Qualify software. The results showed that for premolar and molar teeth, Filtek Supreme showed less wear in bearing cusps, whereas Clearfil APX showed less wear in non-bearing cusps. They concluded that nanocomposite restorations showed significantly less wear at bearing cusps, whereas microhybrid composite restorations showed less wear at non-bearing cusps and anterior maxillary teeth (**Ning et al, 2021**).

Remineralization effect of natural versus synthetic materials on

deep carious dentin was studied. Extracted human molars with class I carious lesions were collected and randomly assigned into four groups: a control group, a propolis-treated group, a hesperidin-treated group, and a group treated with silver diamine fluoride (SDF). Carious tissues were managed using the stepwise caries removal approach, followed by application of the respective test materials. All cavities were then restored using glass ionomer cement (GIC). Radiographic evaluations were conducted at 6 and 12 weeks to assess changes in mineral density. Among the tested groups, the propolis group exhibited the greatest increase in mineral density, while the hesperidin group recorded the lowest with no significant difference. The findings suggested that both propolis and hesperidin demonstrated notable potential in enhancing dentin remineralization and limiting caries progression, presenting viable alternatives to SDF (*Anani et al. 2023*).

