### **4. Research Hypothesis, Aim, Objectives & Expected Outcomes**

#### **a. Hypothesis**

Null hypothesis: There is no significant difference between wear resistance and bioactivity between self cured bioactive RBC and light cured nano-hybrid one.

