#### **II-6- Evaluation of the wear resistance:**

A digital impression will be taken immediately after restoration (T0) using an intraoral scanner (Helios 600 intraoral scanner, Eighteeth, Changzhou, China). To ensure optimal performance and accuracy, the scanner underwent regular calibration before scanning each patient, following the manufacturer's recommendations. During the scanning procedure, the device will be positioned at a 90° angle for the occlusal surface and at 45° angles for both buccal and lingual surfaces. Later on, each restoration will be examined at standardized follow-up periods (Table 2 and 3); six months (T1), twelve months (T2), eighteen months (T3) and twenty-four months (T4). The 3D impressions will be analyzed using a software (Geomagic software, 3D Systems Inc., USA) program and the impressions of each two consultative visits will be superimposed to determine the wear volume loss (mm^3). (Bronkhorst et al, 2022)

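### Two unranked primary outcomes are tested at every visit at P<0.05 under one joint null, with no decisive visit and no rule for rejecting that null

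*Protocol*

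**What the plan says.** Protocol section 2 (Introduction and Background) says that "the primary objectives of this study are to clinically evaluate the wear resistance and the bioactivity of such material". Section 4c lists the two as objectives 1 and 2, with no statement that either takes precedence. Section 4a sets a single null over both: "There is no significant difference between wear resistance and bioactivity between self cured bioactive RBC and light cured nano-hybrid one".

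Under Statistical analysis, the independent t-test or Mann-Whitney test "will be performed for pair wise comparison between groups in each time at P value < 0.05", and the general criterion follows: "P<0.05 is considered significant". No adjustment, testing order or decisive visit is given.

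The visits are fixed elsewhere:
- **Wear (II-6):** a reference scan T0, then scans at 6, 12, 18 and 24 months (T1 to T4). Scans from pairs of visits "will be superimposed to determine the wear volume loss", so there is no wear value at T0.
- **Mineral density (II-7):** readings immediately after restoration (D0), at one month (D1) and at three months (D2).

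The research question (section 3) asks about both outcomes at two years. Each patient receives both materials, one per molar (II-4).

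**The concern.** The protocol does not leave multiplicity open. It prescribes a 0.05 test at each visit for both primary outcomes and attaches all of them to one null. Six post-baseline comparisons bear on that null, or seven if D0 is tested, and the text does not say which result answers the question.

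One isolated significant visit could therefore support a claim that the materials differ. If visits disagree, which is easy with about ten pairs, the choice of visit could be made after seeing the data. The two-year research question does not settle it: the analysis section does not use it for wear, and it cannot apply to density, which is last measured at three months.

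**Working it through.** **The plan's own figure.** Section 6 gives d = 1.22, alpha 0.05, power 80% and 20 restorations (10 per group). For two independent means, the noncentral t gives 10 per group one-sided (power 83.6%), which matches. Two-sided it needs 12 per group, and 10 per group gives 73.2%. Sidedness is not stated. Either way, the trial is sized for a single comparison at 0.05.

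**Number of tests.** Wear has 4 (T1 to T4). Density has 2 after baseline (D1, D2), or 3 with D0. The family is 4 + 2 = 6, or 4 + 3 = 7.

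**Independent tests**, chance of at least one P<0.05 when nothing differs, 1 - 0.95^k:
- 4 wear tests: 1 - 0.95^4 = 18.5%
- 6 tests: 1 - 0.95^6 = 26.5%
- 7 tests: 1 - 0.95^7 = 30.2%

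**Correlated visits.** The documents give no correlations, so these are assumptions. The simulation used 10 patients with both materials in each, no true difference, two-sided t-tests at 0.05, equal correlation between visits of one outcome, and independent outcomes.

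| Visit correlation | Paired, 4 wear tests | Paired, 6 tests | Paired, 7 tests | Independent t, 7 tests, within-patient correlation 0.3 | Independent t, 7 tests, within-patient correlation 0.5 |
|---|---|---|---|---|---|
| 0 | 18.8% | 26.2% | 30.6% | 15.0% | 6.4% |
| 0.5 | 16.1% | 23.8% | 27.0% | 13.6% | 5.8% |
| 0.7 | 13.6% | 21.3% | 23.1% | 11.5% | 5.4% |
| 0.9 | 9.8% | 16.5% | 18.2% | 8.9% | 3.9% |

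The independent t-test with zero within-patient correlation gives nearly the same as the paired test: 30.0% to 17.3% for seven tests and 26.6% to 16.4% for six. Differences of about one percentage point are simulation error.

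The last two columns are the design and test as written. An independent test on positively correlated pairs overstates the standard error of the difference, so each test rejects too rarely and offsets the multiplicity. Pairing the test brings the rate back to the paired columns.

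**One comparison per outcome.** Two independent tests at 0.05 give 1 - 0.95^2 = 9.75%. Holm holds this to at most 5%.

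**The case against.** A reader might infer that this trial, run exactly as written, has a 17-30% chance of a false difference instead of 5%. The documents do not support that. The written plan applies an independent-samples test to within-patient pairs. At a within-patient correlation of 0.5 the seven-test rate is close to nominal, and at 0.3 it is about half the paired figure. This objection stands as a limit on the size. It does not rescue the plan, because the offset comes from a second defect, its size is unknown, and it disappears when the test is paired.

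A reader might also infer that the protocol says any one significant visit rejects the null. It does not; it states no rejection rule at all. Since section 4c lists two objectives, wear and density can fairly be read as separate questions. The relevant rate for wear is then about 10-19%, still well above 5% under a paired analysis.

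The 30% end also requires counting D0, which is a baseline reading. The wording of a test at each time covers it, but without it the ceiling is about 27%.

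Finally, multiplicity and the decisive visit are often left to a SAP, which is not shown here. That would excuse silence. Here the protocol states the per-visit rule itself, for two outcomes it calls primary, so a later adjustment would have to override it. It is fair to say that the research question points to 24 months for wear, but the analysis text does not take that up.

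**Conclusion.** The point holds as a defect in a stated rule: two unranked primary outcomes, one joint null, a 0.05 test at every visit, no decisive visit and no rejection rule.

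The size is conditional. If any significant visit is read as a difference and the analysis is correctly paired, the false-difference chance is about 16-27% over six tests, about 17-30% over seven, and about 10-19% for wear alone. These ranges rest on assumed visit correlations of 0.9 down to 0 and, for the pooled figures, on independent outcomes. If wear is computed between successive scans, the visits may be less correlated, which points to the upper ends.

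Under the independent-samples test as written, the seven-test rate is about 9-15% at a within-patient correlation of 0.3 and about 4-7% at 0.5. The protocol should be corrected before any data are compared, but no single inflated error rate can be attributed to it.

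**What to change.** Amend sections 4a and Statistical analysis as follows:
- Split the joint null into one null for wear and one for bioactivity.
- Name one confirmatory comparison per outcome: wear volume loss from T0 to T4, with the T4 scan superimposed on T0, to match the two-year question; and density change from D0 to D2. Limit the two-year wording in section 3 to wear.
- Analyse both within patient.
- Control error across the two by Holm, or by a fixed sequence with wear first.
- Report all other visits descriptively with 95% confidence intervals.

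This costs a few sentences and no extra patients, visits or measurements. The price is power. The first Holm step is at 0.025, and at d = 1.22 with 10 per group two-sided power falls from 73% to 62% (with 12 per group, from 81% to 72%). Those figures hold only under the protocol's independent-groups model; paired power depends on the unstated within-patient correlation.

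A fixed sequence keeps the full 0.05 for wear, but density is then confirmatory only if wear is significant. Section 4d expects only a slight wear difference and a marked bioactive effect, so the sponsor should weigh this before choosing between the two.
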